3.3. Benefit/Risk Assessment

More information about the known and expected benefits, risks, serious adverse events (SAEs) and reasonably anticipated adverse events (AEs) of ixekizumab are to be found in the IB.

4. Objectives and Endpoints

Table RHCH.1 shows the objectives and endpoints of the study.

Table RHCH.1. Objectives and Endpoints

Objectives	Endpoints

Primary
 
 The primary objective is to compare ixekizumab 80 mg Q4W versus placebo in bDMARD-naïve patients with active r-axSpA at Week 16 	
 Proportion of patients achieving an Assessment of Spondyloarthritis International Society 40 (ASAS40) response

Secondary
 
The major secondary objectives are:
 
 To compare ixekizumab 80 mg Q4W to placebo in overall study population at Week 16 
Other secondary objectives are:
 
 To compare ixekizumab regimen 80 mg Q4W to placebo during the 16-week placebo-controlled period (Period 2) in overall study population 	
 Proportion of patients achieving an ASAS40 response Proportion of patients achieving an ASAS20 response Change from baseline in Ankylosing Spondylitis Disease Activity Score (ASDAS) Change from baseline in Bath Ankylosing Spondylitis Disease Activity Index (BASDAI) Change from baseline in Bath Ankylosing Spondylitis Functional Index (BASFI) Proportion of patients achieving ASDAS < 2.1 Change from baseline in magnetic resonance imaging (MRI) of the spine (Spondyloarthritis Research Consortium of Canada [SPARCC] score) Change from baseline in Short Form 36 (SF-36) physical component score (PCS) Proportion of patients who achieve ASAS20, ASAS40, ASAS 5/6, and partial remission by ASAS criteria Change from baseline in the individual components of the ASAS criteria Change from baseline in BASDAI Proportion of patients reaching BASDAI50 Change from baseline in ASDAS Proportion of patients who experience clinically-important improvement (change of ASDAS from baseline ≥ 1.1) or major improvement (change of ASDAS from baseline ≥ 2.0 or achievement of the lowest possible score) or inactive disease (ASDAS score < 1.3) Change from baseline in the measure of high sensitivity C-reactive protein (CRP) Change from baseline in BASFI Change from baseline in mobility 
 Bath Ankylosing Spondylitis Metrology Index (BASMI) (linear) and individual components Chest expansion Change from baseline in occiput to wall distance


 To determine if the effect of ixekizumab is maintained through Week 52 To measure ixekizumab exposure and assess the relationship between exposure and immunogenicity 	
 Change from baseline in MRI of the SIJ (SPARCC score) Change from baseline in Maastricht Ankylosing Spondylitis Enthesitis Score (MASES) Incidence rate of anterior uveitis or uveitis flares Change from baseline in the following health outcomes measures: Functional Assessment of Chronic Illness Therapy (FACIT) Fatigue Scale, Work Productivity Activity Impairment–Spondyloarthritis (WPAI-SpA) scores, and SF-36 (both PCS and mental component scores [MCS]) and Quick Inventory of Depressive Symptomatology–Self Report 16 items (QIDS-SR16) score 
All endpoints assessed at Week 16 (above) and during the 16-week placebo-controlled period (above) will continue to be assessed through Week 52.
 
In addition, the following endpoint is added:
 
 NSAID intake (ASAS-NSAID score and % of patients taking NSAIDs) Serum trough concentrations of ixekizumab Ixekizumab serum trough concentrations associated with ADA titer sub groups

Exploratory
 
 To evaluate time to first response To compare ixekizumab regimen 80 mg Q4W to placebo during the 16-week placebo-controlled period (Period 2) To evaluate the incidence of anti-ixekizumab antibodies and their relationship to the efficacy of ixekizumab 	
 Onset of action and treatment response (ASAS, ASDAS, CRP, BASFI) during the placebo-controlled period Change from baseline in SPARCC SIJ Structural Score (SSS) Change from baseline in ASAS HI score Efficacy response rates listed below at Weeks 16 and 52 by treatment-emergent anti-drug antibody (TE-ADA) status and by neutralizing anti-drug antibody (NAb) status: 
 Proportion of patients achieving ASAS40 Proportion of patients achieving ASAS20 Proportion of patients achieving ASDAS inactive disease

Note: Other exploratory objectives and endpoints will be specified in the statistical analysis plan (SAP).
	

5. Study Design

5.1. Overall Design

Study I1F-MC-RHCH (RHCH) is a Phase 3, multicenter, randomized, double-blind, placebo-controlled, parallel-group, outpatient study to evaluate the efficacy and safety of ixekizumab 80 mg Q4W SC with starting dose of 160 mg at Week 0 as compared to placebo SC in patients with r-axSpA, during a 16-week Blinded Treatment Dosing Period.

Study RHCH will also evaluate long-term efficacy and safety of ixekizumab during the Extended Treatment Period (Period 3) for a total treatment duration of 1 year (52 weeks).

[figure not shown]
[Figure RHCH.1](#) illustrates the study design; both treatment groups and administration of the investigational product are described in [Section 7.1](#); and the Study Drug Administration Log is described in [Section 7.2.1](#).

All procedures to be conducted during the study, including timing of all procedures, are indicated in the Schedule of Activities ([Section 2](#)). Selected study procedures are to be performed prior to administration of the investigational product, as applicable. [Appendix 2](#) lists the specific laboratory tests that will be performed for this study. Patients discontinuing from study treatment who have received at least 1 dose of investigational product will continue to the early termination visit (ETV) prior to proceeding to the Post-Treatment Follow-Up Period. For the management of patient safety, all patients are to be monitored through the Post-Treatment Follow-Up Period at least as frequently as indicated in the Schedule of Activities ([Section 2](#)).

Excluded and concomitant medications are detailed in [Section 7.7](#).

Pharmacokinetic (PK) sampling is detailed in [Section 9.5](#).

Figure RHCH.1 illustrates the study design.

Abbreviations: LV = last visit; LY = ixekizumab; n = number of patients; Q4W = every 4 weeks; SC = subcutaneous; V = study visit; W = study week.

- a All patients will receive 2 injections at baseline, as detailed in Section 7.1. Patients randomized to the ixekizumab regimen will receive a 160 mg starting dose.
- b All patients will receive 2 injections at Week 16, as detailed in Section 7.1. Patients randomized to placebo at Week 0 will begin ixekizumab 80 mg Q4W at Week 16 with a 160 mg starting dose, and patients randomized to ixekizumab at Week 0 will receive 1 ixekizumab 80 mg injection and 1 placebo injection at Week 16 to maintain the blinding (Section 7.1).
- c Patients who discontinue from study treatment for any reason and who have received at least 1 dose of investigational product will continue to the early termination visit (ETV) before entering the Post-Treatment Follow-Up Period. V801 and V802 are required for all patients (Section 9.4.10).

Figure RHCH.1. Illustration of study design for Clinical Protocol I1F-MC-RHCH.

5.2. Number of Participants

Participants will be screened to achieve 140 randomized participants for an estimated total of 70 evaluable participants per treatment group.

5.3. End of Study Definition

End of the study is the date of the last visit or last scheduled procedure shown in the Schedule of Activities (Section 2) for the last patient in the trial.

5.4. Scientific Rationale for Study Design

Ixekizumab 80 mg Q4W with a 160 mg starting dose will be studied as detailed in Section 7.1. Dose justification is outlined in Section 5.5. The study blind is maintained as described in Section 7.3.

The placebo-controlled Blinded Treatment Dosing Period (Period 2) is designed to minimize bias in the evaluation of ixekizumab in patients with r-axSpA for both efficacy and safety. All patients may still receive treatment in the form of the allowed concomitant medications as described in the study inclusion and exclusion criteria (Sections 6.1 and 6.2) and concomitant therapy (Section 7.7). Patients can be discontinued from study treatment at any time by investigator or patient decision if they are considered to be receiving insufficient benefit from study treatment (Section 8.1).

As of Week 16 (after completion of Period 2), investigators are allowed to adjust some concomitant medications, if needed, as specified in Section 7.7, across all treatment groups.

Patients originally assigned to placebo during Period 2 will receive ixekizumab 80 mg Q4W with a 160 mg starting dose at Week 16.

Ixekizumab 80 mg Q4W is continued beyond Week 16 to further assess safety and efficacy during the Extended Treatment Period (Period 3).

The effectiveness of ixekizumab in treating r-axSpA will be assessed primarily by the ASAS40 response rate in bDMARD-naïve patients at Week 16. ASAS 40 and ASAS20 response will also be assessed in overall study population at Week 16. These measures and the Week 16 endpoint are in alignment with efficacy endpoints for currently approved r-axSpA therapies and with regulatory guidance (EMA 2009). Steady state exposure of ixekizumab is expected to be reached by Week 16. Based on previous studies with ixekizumab in patients with psoriasis, RA, PsA and r-axSpA, maximum or near maximum clinical effect in r-axSpA were achieved within this time frame for ixekizumab treatment (Griffiths et al. 2015; Genovese et al. 2016; Mease et al. 2017; Nash et al. 2017; van der Heijde et al. 2018; Deodhar et al. 2019b).

Baseline C-reactive protein (CRP) has been reported as a predictor of response in patients with r-axSpA treated with TNF inhibitors (Inman et al. 2008; de Vries et al. 2009; Sieper et al. 2011; Vastesaeger et al. 2011); hence, by including it as a stratification factor, it ensures balance in baseline CRP levels, resulting in greater comparability across treatment groups at baseline. Similarly, the prior TNF inhibitors used has been reported to potentially impact response rates of

subsequently used biologics (Lie et al. 2011; Glintborg et al. 2013); therefore, patients will also be stratified based on prior TNF inhibitor experienced or biological naïve. Thus baseline status will produce the following 3 strata:

- 1) AS patients who are biologic naïve and have normal baseline CRP.
- 2) AS patients who are biologic naïve and have elevated baseline CRP.
- 3) AS patients who have demonstrated either intolerance or inadequate response to one TNF inhibitor and have elevated baseline CRP.

The Extended Treatment Period (Period 3) will permit collection of data for the assessments of maintenance of efficacy and long-term safety with ixekizumab.

The Post-Treatment Follow-Up Period (Period 4) is important for safety and efficacy monitoring following administration of the last study treatment.

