10.1. Sample Size Determination

Approximately 140 patients will be randomized at a 1:1 ratio in the Blinded Treatment Dosing Period (Period 2) to ixekizumab 80 mg Q4W with a starting dose 160 mg and placebo.

For 90% power to test the superiority of ixekizumab Q4W to placebo for ASAS40 at Week 16 in bDMARD-naïve patients, at least 61 bDMARD-naïve patients per treatment group would be needed. The following assumptions were used for the power calculations for ASAS40 response rates: 44% for ixekizumab 80 mg Q4W treatment group and 16% for the placebo group in bDMARD naïve patients.

For the key secondary efficacy endpoint ASAS40 response at Week 16 compared to placebo group in overall study population, the power would be >90%. The assumptions are 42% response rate for ixekizumab 80 mg Q4W treatment group and 15% for the placebo group in overall study population.

These assumptions are based on the review of historical clinical studies in r-axSpA (etanercept, adalimumab, infliximab, certolizumab, and golimumab [Davis et al. 2003; van der Heijde et al. 2005, 2006; Inman et al. 2008, Landewé et al. 2014]) and recent secukinumab trials including both TNF inhibitor experienced patients and naïve patients (Baeten et al. 2014b; Sieper et al. 2014).

A 2-sided Fisher's exact test at the 0.05 level is assumed. Sample size and power estimates were obtained from nQuery® Advisor 7.0.

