10.3.10.2. Subgroup Analyses

Subgroup analyses will be conducted for ASAS40 and selective major secondary outcomes (defined in the SAP) at Week 16 (Visit 8) using the ITT Population.

Subgroup analyses may be conducted based on gender, age category, baseline disease severity, baseline CRP status, baseline MRI status, prior TNF inhibitor experience, and presence of HLA-B27.

For ASAS40, a logistic regression model with treatment, subgroup, and the interaction of subgroup-by-treatment included as factors will be used. The subgroup-by-treatment interaction will be tested at the significance level of 0.10. Treatment group differences will be evaluated within each category of the subgroup using Fisher's exact test, regardless of whether the interaction is statistically significant. Missing data will be imputed using NRI as described in Section 10.3.4. If any group within the subgroup is <10% of the total population, only summaries of the efficacy data will be provided (that is, no inferential testing).

For continuous efficacy outcome (for example, mean change from baseline in ASDAS), an ANCOVA model with treatment, baseline value, subgroup, and the interaction of subgroup-by-treatment will be used. The subgroup-by-treatment interaction will be tested at the significance level of 0.10. Treatment group differences will be evaluated within each category of the subgroup using an ANCOVA model with treatment and baseline value as a covariate, regardless of whether the interaction is statistically significant. Missing data will be imputed using the mBOCF method as described in Section 10.3.4.

Detailed description of the subgroup variables will be provided in the SAP. Additional subgroup analyses on efficacy or subgroup analyses on safety may be performed as deemed appropriate and necessary.

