Baseline BASDAI	quantitative summary	
	<4, ≥4 and <6, ≥6	
Baseline Patient global assessment of disease activity NRS	quantitative summary	
Baseline Inflammation (mean of questions 5 and 6 of BASDAI)	quantitative summary	
Baseline Spinal pain (BASDAI question 2)	quantitative summary	
Baseline spinal pain at night due to AS (Pain NRS)	quantitative summary	
Baseline spinal pain due to AS (Pain NRS)	quantitative summary	
Baseline BASFI	quantitative summary	
Baseline BASMI Linear	quantitative summary	
Baseline Chest expansion	quantitative summary (in cm)	
Baseline Occiput-to-wall measurement	quantitative summary (in cm)	

Baseline enthesitis		
Baseline MASES	quantitative summary	
	=0, >0	
Baseline heel enthesitis	=0, >0	
Baseline health outcome measures		
Baseline ASAS HI	quantitative summary	
	<3, ≥3	
	≤5, >5	
Baseline FACIT-F score	quantitative summary	
Baseline EQ-5D-5L	quantitative summary	
Baseline WPAI-SpA	quantitative summary	
Baseline SF36 PCS	quantitative summary	
Baseline SF36 MCS	quantitative summary	
Baseline QIDS-SR16	quantitative summary of total score	
	Item12: 0, 1, 2, 3	
Baseline concomitant therapy use		
Baseline cDMARDs use ^e	yes, no	Yes
Baseline methotrexate use	quantitative summary	
	yes, no	
Baseline sulfasalazine use	quantitative summary	
	yes, no	
Baseline hydroxychloroquine use	quantitative summary	
	yes, no	
Baseline oral corticosteroid use ^e	yes, no	
Previous therapy: axial spondyloarthritis		
Previous non-biologic systemic agent for r-axSpA	yes, no	
Previous non-biologic non-systemic agent for r-axSpA	yes, no	
Previous TNF inhibitor for r-axSpA	yes, no	Yes
Habit		
Tobacco use	never, current, former	Yes
Cigarette use	≤10 per day, > 10 per day	
Alcohol consumption	never, current, former	
Caffeine/xanthine ingestion	never, current, former	
Baseline NSAID (including COX-2 inhibitors) use		
Baseline ASAS-NSAID score	quantitative summary	
Baseline NSAIDs use ^e	yes, no	
Baseline Imaging of Sacroiliac Joints and Spine		
Baseline SPARCC SIJ MRI	quantitative summary	
	<2, ≥2	Yes
Baseline SPARCC SIJ SSS MRI for fat metaplasia	quantitative summary	
Baseline SPARCC SIJ SSS MRI for erosion	quantitative summary	
Baseline SPARCC SIJ SSS MRI for backfill	quantitative summary	

Baseline SPARCC SIJ SSS MRI for ankylosis	quantitative summary	
Baseline SPARCC spine MRI	quantitative summary	
	<2, ≥2	Yes

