6.12. Subgroup Analyses

6.12.1. Efficacy Subgroup Analyses

Subgroup analysis will be conducted for the primary endpoint of proportion of patients achieving an ASAS40 response at Week 16 (NRI) using the ITT Population for the Period 2. The major secondary efficacy endpoint, the proportion of patients achieving ASAS20 (NRI) at Week 16, will also be conducted. Subgroup analysis using the ITT Population in bDMARD-naïve patients may be explored.

For categorical response variables (ASAS20, ASAS40), a logistic regression analysis with treatment, subgroup, and treatment-by-subgroup interaction as factors will be used. The treatment-by-subgroup interaction will be tested at the 10% significance level. Treatment group differences will be evaluated within each subgroup using the Fisher's exact test, regardless of whether the interaction is statistically significant. If any group within the subgroup (for example, yes, no) is <10% of the total population, only descriptive statistics will be provided for that subgroup (that is, no inferential testing).

Forest plots may be created to illustrate the treatment differences with 95% CIs between each of the ixekizumab treatment groups and placebo group, by each subgroup category.

Please see [Table RHCH. 6.1.](#) for subgroups of baseline characteristics that will be analyzed.

Additional subgroup analyses on efficacy may be performed as deemed appropriate and necessary.

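### Because TNF-experienced patients must have elevated CRP, the planned one-factor subgroup contrasts for prior TNF inhibitor use and for CRP partly measure each other

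*Protocol*

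**What the plan says.** Inclusion criterion [4] (Protocol 6.1) admits biologic-naïve patients at any CRP, but TNF-experienced patients only with CRP above 5.00 mg/L. Protocol 5.4 accordingly lists three strata: naïve with normal CRP, naïve with elevated CRP, and "AS patients who have demonstrated either intolerance or inadequate response to one TNF inhibitor and have elevated baseline CRP". Protocol 7.2 and SAP 5.2 set a mix of about 60% elevated and 40% non-elevated CRP, with at least 61 naïve patients per arm.

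Protocol 10.3.10.2 names, among the possible subgroup factors, "baseline CRP status, baseline MRI status, prior TNF inhibitor experience, and presence of HLA-B27". The patient-characteristics table in SAP 6.6.1 marks "Previous TNF inhibitor for r-axSpA" for efficacy subgroup analysis, and also CRP at cuts of 3, 5, 10 and 15 mg/L. For ASAS40 and ASAS20, SAP 6.12.1 states that "a logistic regression analysis with treatment, subgroup, and treatment-by-subgroup interaction as factors will be used". The interaction is tested at the 10% level, with Fisher's exact test within each category. A category with fewer than 10% of patients is only described. On a naïve-only version, the same section says: "Subgroup analysis using the ITT Population in bDMARD-naïve patients may be explored". Neither document mentions the missing combination in connection with the subgroup analyses.

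**The concern.** A one-factor contrast answers its own question only if the two groups are alike in other characteristics that change the treatment effect. Here the eligibility rule makes them unlike. The TNF-experienced group is all CRP-elevated by design, while the naïve group is a mixture. Conversely, the elevated-CRP group holds all the TNF-experienced patients and the non-elevated group holds none.

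If ixekizumab works better at higher CRP, the TNF-experienced group can look as if it does better because of its CRP, or a true deficit after a TNF inhibitor can be cancelled. SAP 6.12.1 foresees forest plots of treatment differences by subgroup category, and readers will compare those estimates directly. What is at stake is the attribution of a difference between subgroups, not the existence of a treatment effect.

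**Working it through.** **Plan's own figure.** Protocol 10.1 states: "For 90% power to test the superiority of ixekizumab Q4W to placebo for ASAS40 at Week 16 in bDMARD-naïve patients", at least 61 per group are needed, assuming "44% for ixekizumab 80 mg Q4W treatment group and 16% for the placebo group in bDMARD naïve patients". It adds: "A 2-sided Fisher's exact test at the 0.05 level is assumed". Exact enumeration of Fisher power gives 89.9% at 60 per group and 90.5% at 61, so 61 reproduces. For the overall population (42% vs 15%, 70 per arm) the power is 93.2%, consistent with the stated figure above 90%.

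**Stratum sizes** (N = 140; 60% elevated; naïve at the minimum of 2 × 61 = 122):
- TNF-experienced/elevated: 140 − 122 = 18, or 12.9%. This is a ceiling, because 61 per arm is a minimum.
- Naïve/normal: 0.40 × 140 = 56.
- Naïve/elevated: 84 − 18 = 66.

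**Mixing shares.** With 1:1 allocation within strata, a pooled risk difference is the size-weighted mean of the stratum risk differences. Let D be the treatment effect in naïve/elevated minus that in naïve/normal, and T the effect in experienced/elevated minus that in naïve/elevated.
- Planned TNF contrast = T + (56/122) × D = T + 0.459 D.
- Planned CRP contrast = D + (18/84) × T = D + 0.214 T.
- With 14 experienced patients the shares are 56/126 = 44% and 14/84 = 17%.
- The contrast within CRP-elevated patients returns T; the contrast within naïve patients returns D.

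These shares are exact on the risk-difference scale and only indicative on the logistic scale of the planned test.

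**Size of the shift.** The documents give no effects by CRP, so D is an assumption. If T = 0, the planned TNF contrast is:

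| D (points) | 10 | 20 | 30 | 40 |
|---|---|---|---|---|
| TNF contrast (points) | +4.6 | +9.2 | +13.8 | +18.4 |

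**Effect on the tests.** Simulation of the planned interaction test at 0.10 with 28/33/9 patients per arm, placebo 16% and an average naïve effect of 28 points. Wald runs with an empty or full cell (about 21% of TNF tests under no interaction) count as non-rejections.

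| Scenario | Test | Planned contrast | Restricted contrast | Rejection by likelihood ratio, planned / restricted | Rejection by Wald, planned / restricted |
|---|---|---|---|---|---|
| No interaction | TNF | 0 | 0 | 13.9% / about 14% | 5.2% / 5.4% |
| D = 30, T = 0 | TNF | +13.8 | 0 | 19.8% / 13.9% | 3.9% / 5.5% |
| D = 30, T ≈ −14 | TNF | about 0 | −14 | 13.9% / 15.1% | 5.1% / 11.2% |
| No interaction | CRP | 0 | 0 | 11.2% / about 11% | 9.1% / 8.8% |
| D = 0, T = −28 | CRP | −6.0 | 0 | 12.5% / 11.3% | 10.3% / 8.9% |

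The point estimates move clearly; the rejection rates move little.

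**The case against.** The strongest reply has several parts.

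- **The main clinical question is untouched.** Whether ixekizumab beats placebo after a TNF inhibitor is answered by the randomised comparison within the experienced group, which is valid as planned. This stands. The restriction changes only the group against which that effect is compared.
- **Power is negligible.** With about 9 experienced patients per arm, the interaction test detects almost nothing in either form. This stands for the tests. It does not correct the estimates.
- **The TNF test may not run.** Below 14 experienced patients (10% of 140) only descriptive results are given. This stands, but the descriptive results mix the two factors in the same way.
- **The combination may not be exactly empty in the data.** The schedule of activities (Protocol Section 2) indicates that the screening CRP or its retest is used for randomisation, whereas analysis baseline is the last value before the first injection, usually Visit 2. At the 10 and 15 mg/L cuts, experienced patients can also fall on both sides. This qualifies the statement that the group is wholly elevated; it does not remove the imbalance.
- **Default adjustment and optional analyses cover it.** SAP 6.2 adjusts for CRP and TNF experience unless otherwise specified, but SAP 6.12.1 specifies a one-factor model. A CRP main effect alone would also leave the CRP-by-treatment difference in the TNF interaction. The naïve-only analysis is optional and cannot help the TNF contrast.

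A reader might also infer that the stratification was built to answer effect-modification questions. Protocol 5.4 gives balance between arms as its purpose and cites both factors as related to response, not as modifiers of the ixekizumab effect.

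**Conclusion.** The point holds as a limited one about interpretation. At the enrolment targets, about 46% of any CRP-by-treatment difference enters the TNF contrast and about 21% of any TNF-by-treatment difference enters the CRP contrast. The shares follow from eligibility and the enrolment targets. Any actual distortion requires that at least one factor modifies the treatment effect, which is an assumption. The TNF contrast is the more exposed; the CRP contrast is only lightly affected.

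Two stronger readings are not supported. First, that the planned tests will often produce false findings or miss real ones because of the mixing: even D = 30 raises TNF rejection only from 13.9% to 19.8% by likelihood ratio, and by Wald it falls from 5.2% to 3.9%. Second, that the sponsor's own rates imply a TNF deficit which the plan would hide. Backing out experienced rates gives (0.42 × 70 − 0.44 × 61)/9 = 28.4% and (0.15 × 70 − 0.16 × 61)/9 = 8.2%, a 20-point effect against 28 in naïve patients. Rounding of the four inputs alone allows ±2 × (0.005 × 70 + 0.005 × 61)/9 = ±14.6 points, so about 6 to 35. The odds ratios are 4.4 and 4.1, almost no interaction on the scale of the planned test.

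The within-subgroup treatment comparisons, the naïve-only CRP-adjusted primary analysis and the multiplicity-controlled family are not affected.

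**What to change.** In SAP 6.12.1, before unblinding:

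1. Assess the TNF-experience interaction within CRP-elevated patients (naïve/elevated vs TNF-experienced/elevated), using the CRP status applied at randomisation. Keep the 10% rule, with descriptive results if the experienced group is too small.
2. For CRP status at the 5.00 mg/L cut, make the bDMARD-naïve analysis planned rather than optional.
3. Report ASAS40 and ASAS20 treatment differences with 95% confidence intervals for the three randomisation strata side by side, labelled exploratory.

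The cost is two sentences and one table, with no new data and no change to alpha. The contrasts use about 84 (66 + 18) and 122 (56 + 66) patients instead of 140. The change will not give the TNF comparison useful power; it makes clear what that comparison measures.
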